Control group: The subjects assigned to the control group will undergo no intervention. The Principal surgeon will perform adhesiolysis by the same traction counter-traction method with urinary catheter put on free drainage throughout the C-section.

If there will be a suspicion of bladder injury in either group, it will be confirmed by performing the retrograde dye test with methylene blue and injury will be repaired by the Principal surgeon.

Crossover

There is no possibility of crossover in this study as subjects will be selected during operation and the women who refuse to be included in either group preoperatively will be excluded from the study before group assignment.

Data collection procedure

Data will be collected at the time of admission (baseline), during surgery, on the 3rd postoperative day, at the time of discharge from the hospital and the end of three month follow-up period (for those enrolled in the study). The subjects will be advised to report for any postoperative fever or micturition problem during follow-up. Their visits will be recorded on follow up form by the study team medical officers specifically trained in correctly interpreting the problems of the subjects and filling the outcome form (See [Outcome](#) Form).

Baseline Data

The entry form will include baseline data consisting of demographic features and characteristics of the subjects recruited in the study. The demographic features will include age, gestational age, parity, socioeconomic status, and the number of previous C-sections. The other characteristics will be the score of adhesions and preoperative postmicturition bladder volume. The allotted random number will be entered in entry form of the subject and will be signed and kept in a locked place by study team manager in the theatre. (See [ENTRY FORM](#))

Outcome

Primary outcomes will be the bladder injury rate, the extent of the injury, operative time, blood loss and proportion of subjects receiving blood transfusion.

The bladder injury: The bladder injury will be detected by direct observation during surgery. The suspected bladder injury will be confirmed with the dye test and will be reported as the bladder injury rate and extent of injury.

- A. Bladder injury rate will be recorded as the percentage of subjects with bladder injury in each group.
- B. The extent of the injury will be analyzed by the size, site and depth of injury.

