 - i. The size of the injury will be measured in centimetres with a sterilized scale.
 - ii. The site of injury can either be the dome of the bladder, the posterior bladder wall, the trigone or one or both ureters.
 - iii. Depth of injury will be taken as layers involved i.e. either involving muscular layer partly or completely with intact mucosa or full depth injury (perforation).
 - iv.

Operative Time: The staff nurse will record the duration of surgery as time in minutes from incision to closure of the skin.

Blood Loss: The estimated blood loss will be determined by the increase in weight of sponges used during the operation, taking 1 gram equal to 1cc of blood and the number of subjects who received blood transfusion during operation.

Secondary Outcomes

Postoperatively, subjects will be assessed for urinary tract infection (UTI), micturition problems, and fistula formation during the hospital stay and for the next three months. Duration of catheterization and hospital stay will also be recorded. The outcome of each subject will be noted on a Performa by assigned medical officers during the hospital stay and the follow-up period and entered in SPSS20 datasheet.

1-Urinary tract infection (UTI) markers will be more than 10pus cells/hpf in urine or urine showing infectious organisms on culture on the third postoperative day.

- A. **Dysuria** will be expressed by the subject as painful micturition using an 11point Numeric Rating Scale ICCs (.673-.825), $r=.7-.99$. (0 No Pain, 1-3 Mild Pain, 4-6 Moderate Pain, 7-10 Severe Pain).
- B. **Other micturition problems** (feeling of incomplete evacuation, frequency, urgency, urethral and extra-urethral incontinence) will be measured subjectively on Likert scale questionnaire (0-never, 1-rarely, 2-sometimes, and 3-often) and analyzed as a composite variable in spss. Urinary retention will be diagnosed if post-micturition bladder volume is >50cc on ultrasonography on the day of discharge from the hospital.

- I. **Feeling of incomplete evacuation:** It is the feeling created by incomplete emptying of the bladder. The subject will be inquired about the feeling of full bladder accompanying it.
- II. **Urgency** will be diagnosed as a sudden urge to urinate.
- III. **Frequency** Needing to pass urine more than seven times in 24hours.

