- IV. **Vesicovaginal or uretro-vaginal Fistula:** In subjects with the complaint of urinary incontinence, the fistula formation i.e. abnormal communication of urinary bladder or ureter with vagina will be ruled out by three swab test and retrograde cystography. The follow up of fistula cases is outside the scope of this study so it will not be included in description or analysis.

C. **Duration of Foleys catheter and hospital stay:** The Foley's catheter will be removed after 24 hours in distension arms of both groups and subjects stay in the hospital for four days. In the bladder injury arms, the catheter will be kept in situ for 7days to give rest to the bladder for the healing of repair of muscularis disruptions, for 10 days in case of repair of perforations smaller than 1cm, and for 14 days for repair of perforations greater than 1cm. After removal of the catheter, the subjects will be kept in the hospital for twelve hours and then discharged if there will have no subjective urinary complaint.

The finding of subjects will be noted on output form by assigned trainees. The participant's first entry on follow up form will be completed on the third postoperative day; second entry will be at the time of discharge from the hospital and last entry at the end of three months postoperative period. In between, they will be advised to visit our team whenever a problem emerges during the postoperative period and their findings will be recorded on the output form. In subjects complaining of urinary incontinence, the fistula formation will be ruled out first by three swab test and then by retrograde cystography. The postoperative visit at the end of 3months will be mandatory. During this visit, all the subjects will be analyzed for postoperative micturition problems and their retrograde cystography will be performed to rule out fistula formation. The subjects with fistula will be referred to the urologist for further management. The last entry at the end of three months will also be mandatory for the inclusion of participant outcome after discharge in results. The participants will be advised to visit the researcher team at the end of 3months period. They will be reminded for their visit on phone call after week if they do not come for follow-up (See [Outcome](#)).

Statistical analysis

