The results of this study will be submitted for publication to an international, peer-reviewed journal, regardless of whether the results are positive, negative or inconclusive concerning the study hypothesis. Authorship eligibility will be based on the recommendations from the International Committee of Medical Journal Editors (ICMJE).

Perspectives of the study

This study is a small, single centred controlled trial. It is among one of the initial studies to test cysto-inflation to prevent bladder injury. If cysto-inflation proves significantly effective in this study, the evidence provided by this study will not be enough in this era of evidence-based medicine. Nevertheless, this research can serve as a foundation to initiate a much larger high-quality multicentre trial in the support of cysto-inflation to prevent bladder injury. This technique if proved effective can also be useful in all fields of pelvic surgery especially urology, urogynecology, and general surgery.

Potential Risks

- Participation in this study poses a risk for breach of confidentiality.
- Catheterization procedure is mandatory in this study. Approximately two out of hundred women may develop a bladder infection. The researchers will use proper sterilization and clean procedure of the insertion of the catheter according to the study protocol to minimize the risk of developing a bladder infection.
- Subjects of the study should not take part in more than one study at the same time as the outcome of the study can be disturbed by this approach.

Problems Anticipated during the study:

- If recruitment of subjects will not be complete during the anticipated study period, then the period of study may be extended from three months to one year or any further time till the recruitment of study is complete.
- In case of any unexpected outcome that may endanger the subject physically or psychologically, the study may be stopped any time.
- As the study is non-funded, the subjects will not be paid for participation in the study. The subjects belonging to the poor socioeconomic group and coming from distant areas will need thorough counselling for compliance to follow up visits.

Acknowledgements: Theatre staff helping in cysto-inflation study will be acknowledged in the publication.

Project Management:

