Feeling of urinary retention	0				1			2			3
Urethral incontinence	0				1			2			3
fistula	No					Yes					

Postoperative Follow up on the day of discharge from hospital

Follow up	No					Yes					
Postoperative Postmicturition bladder volume											
fever	No					Yes					
Dysuria	0	1	2	3	4	5	6	7	8	9	10
Frequency of micturition	0				1			2			3
Urgency of micturition	0				1			2			3
Feeling of urinary retention	0				1			2			3
Urethral incontinence	0				1			2			3
fistula	No					Yes					

Postoperative Follow up from 1-6weeks

Came for follow up	No					Yes					
fever	No					Yes					
Dysuria	0	1	2	3	4	5	6	7	8	9	10
Frequency of micturition	0				1			2			3
Urgency of micturition	0				1			2			3
Feeling of urinary retention	0				1			2			3
Urethral incontinence	0				1			2			3
fistula	No					Yes					

Postoperative Follow up from 6weeks -3months

Came for follow up	No					Yes					
fever	No					Yes					
Dysuria	0	1	2	3	4	5	6	7	8	9	10
Frequency of micturition	0				1			2			3
Urgency of micturition	0				1			2			3
Feeling of urinary retention	0				1			2			3
Urethral incontinence	0				1			2			3
fistula	No					Yes					

Follow up at the end of 3months

Came for follow up	No					Yes					
fever	No					Yes					
Dysuria	0	1	2	3	4	5	6	7	8	9	10
Frequency of micturition	0		1		2		3				
Urgency of micturition	0		1		2		3				
Feeling of urinary retention	0		1		2		3				
Urethral incontinence	0		1		2		3				
Fistula confirmed by retrograde cystography	No					Yes					

Figure 1:

[figure not shown]

Figure1. Consort Diagram. Patient assignment to groups, follow up and analysis

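### Between discharge and three months, micturition symptoms are recorded only when a woman comes because of a problem, and the Outcome Form has no rule for the interim blocks of a woman who did not come, so transient problems are under-recorded.

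*Combined protocol and SAP*

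**What the plan says.** Secondary Outcomes undertakes to assess women for urinary tract infection, micturition problems and "fistula formation during the hospital stay and for the next three months".

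The scheduled contacts are fewer than that implies. Data collection procedure lists admission, surgery, the third postoperative day, and then "at the time of discharge from the hospital and the end of three month follow-up period". The follow-up text under item C of Secondary Outcomes agrees: after the day 3 entry, "second entry will be at the time of discharge from the hospital and last entry at the end of three months postoperative period". Contact between the last two is left to the woman: "In between, they will be advised to visit our team whenever a problem emerges during the postoperative period". Data collection procedure puts it in similar terms: "The subjects will be advised to report for any postoperative fever or micturition problem during follow-up".

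The Outcome Form has two further blocks, headed "Postoperative Follow up from 1-6weeks" and "Postoperative Follow up from 6weeks -3months". Each has an attendance box (No/Yes), then rows for fever, dysuria on the 0-10 scale, frequency, urgency, feeling of retention and urethral incontinence on the 0-3 scale, and fistula. Nothing says how these rows are filled when attendance is No.

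Three other rules bear on this. The three-month visit is mandatory, and all women are assessed for micturition problems there. A woman's post-discharge outcomes enter the results only if she has the three-month entry (item C). Under Statistical analysis, the same problem in the same woman is entered once, and women who do not come for follow-up after discharge are left out of the analysis of results.

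**The concern.** In the interim weeks, having the outcome is what causes it to be recorded. A woman who is well and a woman who has symptoms but stays at home leave the same trace: attendance No and empty rows. The protocol itself expects difficulty here, noting that poorer women and those "coming from distant areas will need thorough counselling for compliance to follow up visits".

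This concerns women who do attend at three months. Those who never return are covered by the exclusion rule, which is a separate missing-data matter.

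At stake is part of the safety comparison. The Background names postoperative micturition problems as the risk of over-distending the bladder. A problem that arises at home and settles before the last visit can be missed in either group, so the count of such problems would be too low and the absolute difference between groups too small.

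**Working it through.** **Step 1. Set schedule against form.**

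| Period | Contact | Who is scored |
|---|---|---|
| Third postoperative day | scheduled | all women |
| Discharge | scheduled | all women |
| 1-6 weeks | only if a problem prompts a visit | women who come |
| 6 weeks to 3 months | only if a problem prompts a visit | women who come |
| End of 3 months | mandatory | all women who attend |

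The gap is the third and fourth rows. The telephone reminder in item C follows the sentence on the three-month visit, so it does not clearly reach the interim windows. The three-month rows of the form state no look-back period.

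**Step 2. What can an empty interim block mean?** The plan leaves two possibilities for a woman who has the three-month entry.

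- (a) No problem. All such women form the denominator, and a problem counts if it was recorded at any visit. The once-per-woman rule and the mandatory three-month entry point this way.
- (b) Missing. An analysis of the block would then use attenders only. No section plans such an analysis, but none rules it out.

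**Step 3. Consequence of each.** The plan gives no figure on this point to reproduce, and no symptom or attendance rate. All rates below are assumptions. Let p be the true interim problem rate, a the attendance of women with a problem, and b the attendance of women without one.

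- Reading (a): recorded rate = p × a.
- Reading (b): recorded rate = p × a / [p × a + (1 − p) × b].

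Take n = 96 per group, from the plan's 107 less its 10% drop-out (107 × 0.9 = 96.3), with p = 15% in control and 30% in cystoinflation. Power is two-sided at 5%, normal approximation: Φ[(d − 1.96 × SE0)/SE1], where d is the difference in rates, SE0 is the pooled and SE1 the unpooled standard error.

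*Reading (a):*

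| a | Recorded rates | Risk ratio | Power |
|---|---|---|---|
| 1.0 | 15% v 30% | 2.0 | 0.70 |
| 0.8 | 12% v 24% | 2.0 | 0.58 |
| 0.6 | 9% v 18% | 2.0 | 0.45 |

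The last row in full: SE0 = √(2 × 0.135 × 0.865/96) = 0.0493; SE1 = √[(0.09 × 0.91 + 0.18 × 0.82)/96] = 0.0489; (0.09 − 1.96 × 0.0493)/0.0489 = −0.14; Φ = 0.45.

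*Reading (b), with a = 1:*

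| b | Attenders per group | Rates among attenders | Power |
|---|---|---|---|
| 0.05 | 18.5 v 32.2 | 78% v 90% | 0.22 |
| 0.20 | 30.7 v 42.2 | 47% v 68% | 0.45 |
| 0 | 14.4 v 28.8 | 100% v 100% | no contrast |

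A second set of assumptions, p = 10% v 20% and a = 0.8, gives the same picture. The true risk ratio of 2.0 becomes 1.00, 1.25 or 1.62 among attenders when b is 0, 0.05 or 0.20. It stays at 2.0 under reading (a), where the rates are recorded as 8% v 16%.

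**Step 4. What the illustration shows.** Under reading (a) the error is under-recording in proportion to a. The ratio holds if a is the same in both groups, while the absolute difference and the power shrink. Under reading (b) both the rates and the ratio depend on how many well women happen to come.

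**The case against.** The strongest answer is that the plan already points to a sound denominator. It specifies no rate or regression by interval. Counting each problem once per woman, and requiring the three-month entry before post-discharge outcomes are used, both suggest all women with that entry. A reader might infer that the post-discharge rates rest on a sample selected by the outcome; the documents do not say so. That would follow only if the interim blocks were analysed on attenders alone, for instance by leaving blanks as missing in SPSS. This part of the objection stands, and it makes under-recording the main fault.

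Other limits also stand:

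- The Background speaks of postoperative micturition problems, especially retention. It does not call them delayed, and retention is measured by ultrasonography on the day of discharge.
- Primary outcomes are intraoperative. Day 3, discharge and three-month assessments are planned for everyone, and fistula is looked for in all women at three months.
- Women and the follow-up medical officer are to be unaware of the group (Blinding), which makes attendance that differs by group less likely.
- The power figures rest wholly on assumed rates and attendance. If every woman with a problem came, reading (a) would lose nothing.

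Two arguments carry less weight. The never-to-often scale could be taken to cover earlier weeks, but no section or form row says so. The adverse-event register, with its open questions, could catch a woman who sought care nearer home. It counts only experiences that led to contact with health care, and it is not the source named for the symptom scores.

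**Conclusion.** The point holds as a gap in ascertainment. Problems that begin after discharge and resolve before three months are under-recorded in women who do not travel, although the protocol undertakes to assess symptoms throughout. The size cannot be derived from the documents. If 60% to 100% of women with a problem attend, the recorded rate is 60% to 100% of the true one, and in the illustration power runs from 0.45 to 0.70. Selection by the outcome is a conditional risk that arises only with an attenders-only analysis. Neither a biased comparison between groups nor any effect on the primary outcomes is shown. This is a cheap improvement to one part of the secondary outcomes.

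**What to change.** At the mandatory three-month visit, ask every woman whether each listed symptom occurred in the 1-6 week window and in the 6 week to 3 month window. Complete any blank interim block from her answers.

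Add to Statistical analysis:

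- The outcome is any new micturition problem between discharge and three months, with a statement of what counts as new.
- The denominator is all women with the three-month entry.
- A symptom in an interim block is coded 0 only if the woman attended or answered and did not have it. Without either, it is missing.
- Interim blocks are not reported or regressed on attenders alone.

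The cost is a few questions at a visit that already takes place and a short addition to the analysis section, with no extra staff or procedure. The downside is recall over up to about three months. Because the women are unaware of their group, that error should be similar in both.

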We will perform Statistical analysis by using IBM spss statistics 20 (SPSS Inc, Chicago, IL, USA). The characteristics of the subjects will be analyzed as continuous data or ordinal data. Normality of continuous data will be analyzed by the Shapiro Wilk test. The normal baseline data will be compared by T-test, non-normal data by Mann Whitney U test and ordinal data with the chi-square test. The outcome of both groups will be calculated as numbers (percentages) by descriptive statistics. The effect of cysto-inflation on outcome data will be analyzed using regression analysis. The same problem experienced by the same subject will be recorded only once on the spss datasheet. There will be no second entry if the subject presents with the same problem again. The data for any subject who do not come for follow up after discharge will be used and analyzed in study characteristics but will be excluded from the analysis of results. The power of the study for bladder injury will be calculated with statistical software G'Power version 3.1.

Adverse events

The study team will be responsible to record all adverse events and serious adverse events to the subjects of the study, related to or not related to the intervention. The team members will ask open probing questions to enhance the quality of the collected data. An adverse event is

defined as any undesirable experience during follow-up leading to contact with the healthcare system (general practitioner or hospital). If adverse event results in hospitalisation, prolonged inpatient hospital care, result in re-surgery, or if an adverse event is life-threatening, result in death, permanent disability or damage, they will be categorised as serious adverse events. Adverse Events will be recorded in the adverse events reporting register. The study team will report all expected and unexpected adverse events in the study population to the principal investigator in monthly meetings to assess their potential consequences.

Data Management Plan

Documents safety

All the documents, together with the numbered envelopes and the completed forms will be stored in folders that will be kept in the locked research office of the principal investigator with access limited to authorised persons. The study team will ensure that all variables from the completed forms are continuously entered into SPSS 20 datasheet.

Data monitoring

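### The Statistical analysis section drops women who miss follow-up from all results, with no outcome exempted, although every primary outcome is recorded in theatre; Secondary Outcomes states a narrower rule

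*Combined protocol and SAP*

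**What the plan says.** Two sentences in the combined protocol and SAP decide who enters the results.

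- **Statistical analysis.** The data of women that "do not come for follow up after discharge will be used and analyzed in study characteristics but will be excluded from the analysis of results". No outcome is exempted and no particular visit is named.
- **Secondary Outcomes, closing paragraph.** "The last entry at the end of three months will also be mandatory for the inclusion of participant outcome after discharge in results". The three-month visit is called mandatory, and women who do not come are reminded by telephone.

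The word 'characteristics' is used under Baseline Data for entry-form material: "The entry form will include baseline data consisting of demographic features and characteristics of the subjects recruited in the study".

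The timing of the outcomes is clear:

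- Bladder injury: "The bladder injury will be detected by direct observation during surgery". Its extent (size, site, depth) describes the same finding.
- Operative time: "The staff nurse will record the duration of surgery as time in minutes from incision to closure of the skin".
- Blood loss comes from the weight of sponges used in the operation, together with "the number of subjects who received blood transfusion during operation".
- Urinary tract infection is defined by pus cells or by "urine showing infectious organisms on culture on the third postoperative day".
- "Urinary retention will be diagnosed if post-micturition bladder volume is >50cc on ultrasonography on the day of discharge from the hospital".

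Sample size gives 107 women per group (214 in total), including a 10% allowance for drop-out. The Project summary calls the technique effective if the injury proportion is below half that of the control group.

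**The concern.** Every primary outcome is complete when the operation ends, and two in-hospital secondary outcomes are complete by discharge. None of them depends on a later visit. The analysis sentence nevertheless separates baseline characteristics from results and keeps a non-returner only in the former. A statistician who applied it as written would remove observed primary data because of something that happened afterwards.

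A statistician who applied the Secondary Outcomes sentence would keep those data. The analysis set for every primary outcome therefore depends on which sentence is followed, and the visible text defines no all-randomised set that would settle it. Missed visits are foreseeable: the section on anticipated problems expects that poorer women and those from distant areas will need thorough counselling to attend.

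**Working it through.** **1. The two rules side by side**

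| | Statistical analysis | Secondary Outcomes |
|---|---|---|
| Trigger | Not coming for follow-up after discharge; no visit named | No entry at three months |
| What is lost | The analysis of results, nothing exempted | Outcomes after discharge |
| Theatre, day-3 and discharge outcomes | Lost, read literally | Kept |

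A woman seen at four weeks but not at three months shows the difference in trigger. She has come for follow-up under the first rule but fails the condition of the second. The Outcome Form has separate panels for 1–6 weeks, 6 weeks–3 months and the end of three months, so this case can occur.

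**2. The plan's own figure**

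The 107 per group cannot be reproduced as a two-group calculation, because no injury rate for women with dense adhesions is given. A finite-population survey formula with N = 400 from Sample size, and an assumed 5% margin and 50% proportion, gives 400 × 9604 / (399 × 25 + 9604) = 196.2, rounded up to 197. With 10% drop-out this becomes 217 (× 1.1) to 219 (÷ 0.9), or 109 to 110 per group. That is close to 107, but it rests on assumed inputs and contains no power term. The stated 107 is taken as given below.

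**3. Women affected**

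If the 10% is non-attendance after discharge: 0.10 × 214 = 21.4 women, and 0.90 × 107 = 96.3 per group.

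**4. Precision, if loss is unrelated to injury**

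Control rate p is assumed, with a true rate of p/2 under cystoinflation.

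- Injuries discarded: 10.7 × (p + p/2) = 16.05p.
- Power, two-sided 5%, normal approximation: Φ{[(p/2)√n − 1.96√(2m(1−m))] / √[p(1−p) + (p/2)(1−p/2)]}, where m = 0.75p.
- Example, p = 30%: n = 107 gives (0.15 × 10.344 − 1.96 × 0.5906)/0.5809 = 0.678, or 75.1%. n = 96 gives (0.15 × 9.798 − 1.96 × 0.5906)/0.5809 = 0.537, or 70.5%.

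| Assumed control rate | Injuries discarded | Power, 107 per group | Power, 96 per group |
|---|---|---|---|
| 4.49% | 0.7 | 14.6% | 13.6% |
| 10% | 1.6 | 28.3% | 25.9% |
| 20% | 3.2 | 53.6% | 49.2% |
| 30% | 4.8 | 75.1% | 70.5% |
| 35% | 5.6 | 83.4% | 79.2% |

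The 4.49% is the highest rate quoted in the Background. It is for sixth caesarean deliveries, which is a different population. Standard errors rise by √(107/96) = 1.056, or 5.6%. At p = 30% the 95% limits around a ratio of 0.50 widen from 0.29–0.85 to 0.28–0.88.

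**5. Bias, if loss is related to injury**

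Assume true rates of 30% and 15%, with 30% of injured and 5% of uninjured women lost in both groups.

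- Control: 0.30 × 0.70 / (0.30 × 0.70 + 0.70 × 0.95) = 0.210/0.875 = 0.240.
- Cystoinflation: 0.15 × 0.70 / (0.15 × 0.70 + 0.85 × 0.95) = 0.105/0.9125 = 0.115.
- Ratio: 0.115/0.240 = 0.48, against a true 0.50.

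So the risk ratio moves even when the loss pattern is the same in both groups. A pattern that differed by group could move it further.

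**The case against.** The strongest reply is that the two sentences are easily harmonised. The Secondary Outcomes rule comes just before the analysis section. The sentences immediately before the disputed one deal with repeat complaints by the same woman, which arise mainly at follow-up visits. On that reading, results means results after discharge and no theatre outcome is lost. The equation of study characteristics with entry-form data is an inference, and Figure 1, captioned as showing follow-up and analysis, is not reproduced in the text reviewed and may settle the matter. All of this stands as a possible account of the intent. It does not remove the conflict, because nothing visible subordinates one sentence to the other, and the independent statistician would work from the analysis section.

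It is also fair that the loss is modest, that the mandatory visit and the telephone reminder should limit it, that Sample size does not say its 10% means missed visits, and that the injury rates above are assumed.

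A reader might infer three stronger things that the documents do not support:

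- **That the plan certainly intends to discard primary data.** The intent is unclear.
- **That the trial falls short of its planned size for this reason.** The 107 per group already allows for 10% drop-out.
- **That the comparison will be biased.** The documents give no evidence that attendance depends on injury or on group, and both the women and the follow-up officer are to be unaware of allocation.

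**Conclusion.** The point holds as a conflict between two stated rules, and it should be fixed before analysis. Confidence is high for the mismatch in wording. It is lower for the claim that primary data would in fact be dropped, which depends on following the analysis sentence literally.

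On the literal reading, and if 10% of women miss follow-up, about 21 women with fully observed theatre outcomes leave the primary analysis. If that loss is unrelated to injury, the cost is precision only: about 1 to 5 points of power over assumed control rates of 4.49% to 35%. That is margin given up, not a failure to meet the stated size. If loss is related to injury, the risk ratio used as the effectiveness criterion can shift. The example of 0.50 becoming 0.48 is illustrative and rests on assumed loss rates.

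**What to change.** Replace the exclusion sentence in Statistical analysis with wording such as:

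> All randomised women will be analysed in the group assigned for bladder injury, operative time, blood loss, transfusion, and day-3 and discharge outcomes, whether or not they return; extent of injury will be described for all women with an injury. A woman without the three-month entry will be excluded only from analyses of outcomes at three months; problems recorded at earlier visits after discharge will be retained and reported, with the number missing given by group. Micturition problems up to discharge and after discharge will be analysed separately.

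Align the three-month sentence in Secondary Outcomes with this. Left unchanged, it would still drop problems recorded at the 1–6 week or 6 week–3 month visits for a woman who misses the last one. Check that Figure 1 shows the same analysis sets.

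The cost is a few sentences. The theatre, day-3, discharge and interim findings already have places on the Outcome Form, so nothing new is collected. The only consequence for reporting is slightly different denominators for in-hospital and later outcomes.
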